3.4 Outcome Measures/Endpoints

Primary outcome:

• Ordinal shift in modified Rankin Scale (mRS) at 6 months.

Secondary outcomes:

- Hospital Anxiety and Depression scale at 6 months (HADS)³⁶
- Fatigue score (GM-SAT Fatigue question and Fatigue Severity Score)
- EQ-5D-5L score at 6 months³⁷
- Correlation of the effect of treatment on clinical outcome with its effect on plasma IL-6 concentration

3.4.1 Primary outcome

We will assess the effect of intervention on the mRS (a 7 point ordinal measure of disability from 0 (no symptoms) to 6 (dead)) at 6 months following randomisation.

We have reviewed other clinical outcome measures studied in aSAH including the landmark ISAT trial²⁹ which used GOS-E as primary outcome measure. More recent studies, including STASH¹⁴ and the ongoing ISAT II trial use the mRS. The proposed TOPSAT study being coordinated from the University of Newcastle will also use mRS as primary outcome. mRS is the outcome of choice in ischaemic stroke studies. Both mRS and GOS-E measure disability, i.e. the ability of a person to look after themselves. We have reviewed both of these outcome measures with our PPI group who felt the mRS better described their symptoms following aSAH. The mRS should also give finer discrimination among participants with "Good Recovery" as assessed by the GOS-E. We have experience of using both tools at phase II (GOS-E in our aSAH study and mRS in our ischaemic stroke studies) and find that mRS is much easier to complete and includes all activities of daily living. mRS is well validated including for use over the phone. We have therefore opted to use mRS as primary outcome in our proposed study.

3.4.2 Secondary Outcomes

We will measure quality of life, mood and fatigue as we know that fatigue and mood are the best predictors of poor outcome following aSAH⁶. We will also assess correlation between the effect of treatment on clinical outcome and the effect of treatment on plasma IL-6 concentration.

- 1. Mood: We will explore mood using the HADS³⁶ which is well validated in screening for anxiety and depression. This scale is widely used as an outcome measure, validated for telephone completion and is widely used clinically in people with aSAH.
- 2. Quality of Life: We have chosen EQ-5D-5L as a patient reported quality of life measure following advice from our patient user group. This is a well validated measure³⁷ that has been used in various types of stroke and subarachnoid haemorrhage. The EQ-5D-5L is also used by NICE for reference case analyses (www.euroqol.com).
- 3. Fatigue: We will screen for the presence of post aSAH fatigue with a single question "Do you feel tired all the time or get tired very quickly since your stroke?" which was developed in conjunction with community dwelling stroke survivors and their carers as part of the development of the GM-SAT³⁸. This question identified fatigue as the most common problem (34%) in people 6 months post stroke, a proportion which is consistent with the proportion of stroke patients with post stroke fatigue (33%) as identified by a formal case definition of post stroke fatigue in a longitudinal cohort study³⁹ and with the proportion of people with aSAH who identified feeling tired on a daily basis (31%)⁴⁰.

The GM-SAT fatigue question has now been used to screen for post stroke fatigue in a feasibility intervention study by Wu and colleagues (Wu, S, PhD University of Edinburgh). It is a simple and unambiguous question which can easily be answered as part of a telephone assessment. We will also measure the Fatigue Severity Score which is validated in stroke and takes 2-3 mins to complete³⁸.

4. TRIAL DESIGN

The trial design is a double-blind, randomised, placebo-controlled, multi-centre, parallel group phase III trial.

5. TRIAL SETTING

Up to 1000 patients with SAH will be recruited from up to 20 secondary/tertiary neurosurgical centres in the UK (a list of the participating sites can be found on clinicaltrials.gov). Adults admitted to a participating neurosurgical centre with a clinical diagnosis of acute SAH will be considered for trial participation. The care for all patients in the trial will be identical to the standard care pathway which will continue as normal including diagnosis of the aneurysm by imaging, endovascular coiling or clipping of the aneurysm, intensive or high dependency care, oral nimodipine, rehabilitation, clinical follow-up. No treatment will be withheld as a result of participating in the trial and participation will not affect clinical care.

6. ELIGIBILTY CRITERIA

6.1 Inclusion criteria

- Patients with CT positive spontaneous SAH admitted to a participating neurosurgical centre where written informed consent can be obtained and study drug can be administered within 72 hours of ictus.
- 2. No concomitant health problems that, in the opinion of the PI or designee, would interfere with participation, administration of study drug or assessment of outcomes including safety. Please see precaution of use section 8.1.5 for further guidance.
- 3. Willing and able to give informed consent or consent available from a patient representative for trial inclusion including agreement in principle to receive study drug and undergo all study assessments.
- 4. Male or female aged 18 years or above.

6.2 Exclusion criteria

- 1. Unconfirmed or uncertain diagnosis of spontaneous SAH.
- 2. Known active tuberculosis or active hepatitis.
- 3. Known active malignancy.
- 4. Known Still's Disease
- 5. Neutropenia (ANC $< 1.5 \times 10^9/L$).
- 6. Abnormal renal function (creatinine clearance or estimated Glomerular Filtration Rate (eGFR) < 30 ml/minute) documented in the last 3 months prior to this SAH.
- 7. Live vaccinations within the last 10 days (please see appendix 1) of this SAH.
- 8. Previous or concurrent treatment with IL-1Ra known at the time of trial entry or previous participation in this trial.
- 9. Current treatment with TNF antagonists (please see section 8.1.4 for the prohibited medication).
- 10. Known to have participated in a clinical trial of an investigational agent or device in the 30 days prior to ictus.
- 11. Known to have participated in a clinical trial of an investigational agent or device within 5 half-lives (of the previous agent or device) prior to ictus.
- 12. Known to be pregnant or breast feeding or inability to reliably confirm that the patient is not pregnant (Please see further guidance on pregnancy prevention in section 7.2.1).
- 13. Clinically significant serious concurrent medical condition, pre morbid illnesses, or concurrent serious infection, at the Pl's (or designee's) discretion, which could affect the safety or tolerability of the intervention. Please see precaution of use section 8.1.5 for further guidance.
- 14. Known allergy to IL-1Ra or any of the excipients listed in the drug SmPC (please section 8.1.4).
- 15. Known allergy to other products that are produced by DNA technology using the micro-organism E. coli (i.e. *E.coli* derived protein).

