The drug Summary of Product Characteristics (SmPC) states that IL-1Ra should not be administered in renal failure (Creatinine clearance < 30ml/min) or in neutropenia (absolute neutrophil count (ANC) < 1.5×10^9 L). Blood will be taken and results medically reviewed prior to inclusion in the trial. Injection site reactions may occur with IL-1Ra administered SC but we have found that by administering the injections in different anatomical sites each time these are generally well tolerated; just two patients (n=68 receiving IL-1Ra) withdrew from our phase II study because of injection site reactions. All adverse events will be reported.

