7.2.1 Patient Identification and Screening

The clinical team looking after the patient will make the initial approach to the potential participants or their personal legal representatives (if the patient lacks capacity) and ask if they would consider participation in a research trial. Any potential participant or their personal legal representative who expresses an interest and who is thought to be eligible (see 2.1) to participate will be referred to the research team. Basic demographic, clinical and radiological data will be checked against the eligibility criteria in section 6 to determine whether the potential participant may be eligible for entry into the trial. An anonymous record will be kept within the site file of all those screened which will include, age, sex, date of screening and reason for non-inclusion.

A member of the research team will visit the potential participant or their personal legal representative in the clinical areas to discuss what participation in the trial involves. Once this has been discussed, the researcher will again confirm eligibility before proceeding further. Those who are considered to be eligible to participate and who express an interest in participation will also be given written information containing full details of the trial which they must read before giving their consent.

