7.7 Trial Assessments

7.7.1 Pre-randomisation evaluation

At screening, research staff will review patient health records to confirm eligibility according to the eligibility criteria in section 6. This will include basic demographics (age), past clinical history and radiological data. No identifiable participant data will be recorded. An anonymised screening log will be maintained. Following consent, participants will undergo a baseline assessment which will include transcription of source data including baseline research blood sampling, demographics (date of birth, sex, treating centre), and past clinical & medical history (date and time of ictus; World Federation of Neurological Societies (WFNS) grade at first presentation; pre-morbid mRS; pre-morbid risk factors (including smoking, hypertension, diabetes, ischaemic heart disease); existence of pre-morbid anxiety, depression or fatigue). A 10ml baseline blood sample will be taken immediately following consent and before randomisation for measurement of plasma IL-6. Sampling will be undertaken to ensure the minimal inconvenience to the patient and wherever possible blood will be sampled from an established central venous or arterial line. Where possible, research bloods will be taken at the same time as clinical bloods. Clinical reports of renal function and full blood count will be checked by an appropriate member of the PI team prior to randomisation (see exclusion criteria). Additional tests of full blood count, renal function, and liver function will be performed at the discretion of the clinical team as part of the direct clinical care and will be reviewed at the pre-specified post-randomisation evaluations as detailed below.

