8.1.5 Special warning and precautions for use

Please see current approved version of the SmPC for full details of these events below.

Allergic reactions:

Allergic reactions, including anaphylactic reactions and angioedema have been reported uncommonly. The majority of these reactions were maculopapular or urticarial rashes.

If a severe allergic reaction occurs, administration of study drug should be discontinued and appropriate treatment initiated.

Hepatic events:

Investigators should exercise caution when administering study drug to patients with a history of severe hepatic impairment or liver dysfunction, defined as total bilirubin above the ULN (excluding patients with Gilbert's syndrome), AST or ALT >3 times the ULN or alkaline phosphatase >2.5 times the ULN.

Renal impairment:

Study drug should be used with caution in patients with moderate renal impairment (creatinine clearance or eGFR 30 to 59 ml/minute).

Serious infections:

Investigators should exercise caution when administering study drug to patients with a history of recurring infections or with underlying condition which may predispose them to infections (e.g. Asthma).

When diagnosing infection in a patient in the study, investigators should not rely solely on the CRP level as reduction in plasma CRP has been seen in patients receiving IL-1Ra. However, the reduction is modest and therefore unlikely to impact on clinical decision making.

Consideration should be given to the higher risk of infection in all grades of aSAH patients compared to the normal population (e.g. the RA patient referenced in the SmPC). It is important to note that there is no evidence in the SmPC or from our previous trials (see section 0 for more detail) to support withdrawal of study drug in the event of a serious infection in this population. The decision to interruption or stop IL-1Ra is at the discretion of the local investigator.

Neutropenia:

Events of neutropenia have been observed in previously RA studies when administered long-term. Therefore precaution is recommended in patient with a history of neutropenia.

If a participant becomes neutropenic (ANC < $1.5 \times 10_9$ /I) the ANC should be monitored closely and study drug should be discontinued.

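### Exclusion criterion 6 counts only renal values recorded before the SAH, so an admission creatinine clearance or eGFR below 30 ml/minute triggers no fixed exclusion

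*Protocol*

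**What the plan says.** Section 6.2, criterion 6, sets the renal exclusion at creatinine clearance or eGFR below 30 ml/minute and limits it to values "documented in the last 3 months prior to this SAH". Criterion 5, on neutropenia, stands next to it and has no time window.

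Section 2.2 reports from the product information that "IL-1Ra should not be administered in renal failure (Creatinine clearance < 30ml/min" and pairs this with the neutropenia limit. It then states the safeguard: "Blood will be taken and results medically reviewed prior to inclusion in the trial".

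Section 7.7.1 sets out the check made before allocation: "renal function and full blood count will be checked by an appropriate member of the PI team prior to randomisation (see exclusion criteria".

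Two other eligibility rules could apply. Inclusion 2 rests on the PI's or designee's opinion about health problems that "would interfere with participation, administration of study drug or assessment of outcomes including safety". Exclusion 13 leaves to the PI's or designee's discretion serious conditions "which could affect the safety or tolerability of the intervention". Both refer to section 8.1.5, whose renal text reads: "Study drug should be used with caution in patients with moderate renal impairment (creatinine clearance or eGFR 30 to 59 ml/minute". For further detail that section refers to the product information.

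The synopsis gives the renal exclusion without a time window, but it is an abbreviated summary.

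**The concern.** Section 2.2 presents a current blood sample as the means of keeping patients below 30 ml/min off the drug. The operative rule in section 6.2 looks only at results from before the bleed. Section 7.7.1 then sends the reader from a current renal result to the exclusion criteria, and the one criterion with a renal threshold does not accept that result.

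Patient safety is at stake. Under section 7.2.1, "clinical and radiological data will be checked against the eligibility criteria in section 6", and under section 7.4.1 eligibility is confirmed in the randomisation system before allocation. A patient below the protocol's own dosing limit on the admission sample could be confirmed as eligible unless someone invokes a discretionary criterion.

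**Working it through.** The protocol gives no figure to reproduce here. The check is of the rules against each other, plus simple arithmetic for exposure.

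**Step 1: apply criterion 6 to the possible cases.**

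| Pre-SAH value (last 3 months) | Admission value | Excluded by criterion 6? | Below the limit cited in 2.2 at entry? |
|---|---|---|---|
| < 30 | < 30 | Yes | Yes |
| None on record | < 30 | No | Yes |
| ≥ 30 | < 30 | No | Yes |

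In the second and third rows the current value is below the limit in section 2.2, yet criterion 6 is not met.

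**Step 2: look for another rule with a fixed renal cut-off that such an admission value would trigger.**

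- Criterion 6: no, pre-SAH values only.
- Inclusion 2: no cut-off, a matter of opinion.
- Exclusion 13: no cut-off, a matter of discretion.
- Section 8.1.5: advises caution from 30 to 59 ml/minute, sets no rule of its own below 30, and refers to the product information.

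The count is 0. Section 2.2 does state the limit, but as background to the risk assessment and not as an eligibility criterion.

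**Step 3: compare with neutropenia.** Section 2.2 treats the two limits as a pair, and section 7.7.1 has both results checked. A current neutrophil count can trigger criterion 5. A current renal result cannot trigger criterion 6. The treatment-stopping list in section 7.8 also names neutropenia but has no renal threshold, so no fixed rule catches the patient later.

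**Step 4: scheduled exposure for a patient enrolled this way and allocated to active drug.** Inputs: 100 mg twice daily, nominally every 12 hours; first dose within 72 hours of ictus; stop at 21 days from ictus (synopsis and section 8).

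- Daily dose: 2 × 100 mg = 200 mg.
- First dose at 72 hours (3 days): (21 − 3) × 2 = 36 doses.
- First dose close to ictus: 21 × 2 = 42 doses.

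These are maxima. Discharge from the neurosurgical centre or a decision to stop would shorten them. Allocation is 1:1, and patients on placebo are not exposed.

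**Step 5: how many patients.** This cannot be derived. Table 4 lists renal failure as common (at least 1/100 and below 1/10) among events of the SAH disease process. That covers the whole disease course and gives no rate at admission. It shows only that the protocol expects renal failure in this population.

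**The case against.** The best defence is that clinicians already stand between this wording and a dosed patient. A member of the PI team must look at renal function before randomisation, section 2.2 states the limit and requires medical review of the bloods, and inclusion 2 and exclusion 13 let the PI or designee refuse entry. The cross-reference in 7.7.1 is to the exclusion criteria in general, so an admission value below 30 could count under exclusion 13. The clinical reports checked there may also include results from before the SAH. A caution band of 30 to 59 makes sense only if lower values are already ruled out, and 8.1.5 points to the product information. A medically qualified team member then prescribes, and bloods are reviewed again at days 3-5 and 10-12 and on the final treatment day. The window might even be deliberate, aimed at established renal disease, with acute changes left to judgement.

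Much of this stands as mitigation. Enrolment is not forced, the 7.7.1 check is not empty, and the dose range above is simply the full schedule for any participant.

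It does not remove the defect. Every safeguard listed is discretionary or indirect, whereas neutropenia, its pair in section 2.2, has a fixed rule. Nothing in the protocol explains a window limited to chronic disease, and section 2.2 does not separate acute from chronic impairment. If the window were deliberate, the current renal result checked under 7.7.1 would have no fixed criterion to meet.

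**Conclusion.** The concern holds. As worded, criterion 6 does not exclude a patient whose only value below 30 ml/minute is the admission result, and no other rule with a fixed renal cut-off does so. This conflicts with the limit and safeguard in section 2.2 and leaves the renal half of the 7.7.1 check dependent on discretion.

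The conclusion rests on the plain reading that a sample drawn after ictus is not prior to the SAH. It does not assume that investigators would in fact enrol such patients, only that the text lets them confirm eligibility truthfully. The number affected is unknown and probably small. The point should be fixed because it concerns a dosing limit the protocol itself cites and costs little to correct. It has no direct effect on the sample size or the analysis.

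**What to change.** Reword criterion 6 along these lines: *creatinine clearance or eGFR < 30 ml/minute on the most recent result before randomisation (including the admission sample), or on any result documented in the 3 months before this SAH*. In section 7.7.1, name criteria 5 and 6 in the cross-reference. Align the summary of eligibility in the synopsis.

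The cost is one wording amendment and one line in the eligibility checklist. No extra sampling is needed, since renal results are already reviewed before randomisation. A few patients with acute renal impairment on admission may be excluded who could otherwise have entered; the protocol gives no figure from which to estimate how many.

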7. TRIAL PROCEDURES

7.1 Schedule of Assessments

Table 1 Schedule of Assessments

Reason	Action	Time point of assessment								
		Screening Visit ^d	Entry (consent visit) ^d	Prior to each administration of study drug	From randomisation until final day of study treatment	Day 3-5 post randomisation	Day 10-12 post randomisation	Final day of treatment ^e (<21 days post ictus)	Day 30 post randomisation ^a (+/- 3days)	Month 6 (post randomisation ^b (+/- 28 days)
Eligibility	Eligibility screen	X								
Liigibility	Pregnancy test	X								
	Consent		x							
Baseline characteristics	* Demographics		x							
	# Past clinical history		х							
Mechanism	Research blood (IL-6)		x			х				
	Randomisation		х							
Treatment	Twice daily administration of study drug				х					
Treatment fidelity	Research blood (IL-1Ra)					х				
Safety	Review of clinical blood results by research staff	х				Х	х	x	х	
	Ongoing review of clinical condition by clinical staff			X	Х					
	Research staff review of clinical data for adverse events					x	x	х	x	

	Telephone AE check					х	
Data for collection	Survival check			х	х	х	
	^ Target aneurysm details			х		х	
Efficacy	Outcome Assessments: HADS						x
	Outcome Assessments: Fatigue (GM-SAT fatigue						х
	Outcome Assessments: EQ-5D-5L						х
	Outcome assessment:						х
	Outcome assessment: Survival check ^c						х

Assessment logistics:

- a) Day 30 safety assessment will be performed by the local research team for any participants still an in-patient. Patients who have been discharged to their own home will be contacted directly by telephone by local research team.
- b) The 6 month outcome assessments will be performed by telephone, where possible, and will be coordinated centrally.
- c) A survival check will be performed by contacting the participant's general practitioner to avoid any distress to next of kin.
- d) Clinical CT angiography will be performed in accordance with local clinical practice. This may occur before or after randomisation
- e) Additional clinical data including aneurysm location and treatment will be recorded on final day of treatment

Data to be recorded (full details available in section 7.7):

^ Target aneurysm details — confirmation, position and treatment at day 3-5 and details of rebleed, cerebrospinal fluid (CSF) diversion, delayed cerebral ischaemia (DCI) and CSF infection by day 30.

7.2 Recruitment

Adults admitted to a participating neurosurgical centre with a clinical diagnosis of SAH will be considered for trial participation.

^{*} Demographics – date of birth, sex, treating centre

^{*} Past clinical history – Date and time of ictus, World Federation of Neurological Society grade (WFNS) at first presentation, pre-morbid mRS, pre-morbid risk factors (smoking, hypertension, diabetes, ischaemic heart disease), pre-morbid anxiety, depression and fatigue

7.2.1 Patient Identification and Screening

The clinical team looking after the patient will make the initial approach to the potential participants or their personal legal representatives (if the patient lacks capacity) and ask if they would consider participation in a research trial. Any potential participant or their personal legal representative who expresses an interest and who is thought to be eligible (see 2.1) to participate will be referred to the research team. Basic demographic, clinical and radiological data will be checked against the eligibility criteria in section 6 to determine whether the potential participant may be eligible for entry into the trial. An anonymous record will be kept within the site file of all those screened which will include, age, sex, date of screening and reason for non-inclusion.

A member of the research team will visit the potential participant or their personal legal representative in the clinical areas to discuss what participation in the trial involves. Once this has been discussed, the researcher will again confirm eligibility before proceeding further. Those who are considered to be eligible to participate and who express an interest in participation will also be given written information containing full details of the trial which they must read before giving their consent.

It will be assumed that all women under the age of 55 are of child-bearing potential unless evidence contrary to this can be established from a reliable source. It will be necessary to exclude pregnancy in any woman of child-bearing potential (WOCBP, see list of definitions) prior to entry into the trial. If this cannot be excluded by the potential participant, verbal consent will be sought from the patient or their personal representative and noted in the patient's medical notes for a pregnancy test to be performed prior to consent. If no personal representative is available a professional representative will be asked to give verbal consent for a pregnancy test to be performed to enable determination of the patient's eligibility for the study. During study participation standard practice in regards to the administration of contraception should be followed. Participants enrolled in the study will only be administered IL-1Ra while being an in-patient and the half-life of SC IL-1Ra is 4-6 hours. It is therefore very unlikely that participants who are WOCBP will become pregnant while being exposed to the study drug. Nevertheless the investigator must ensure that all participants are made aware of the potential dangers of being pregnant during their participation in the study. All potential participants will be advised of the need to comply with highly effective contraceptive methods, once permitted to restart contraceptive treatment, for the remaining of the duration of study drug and up to 30 hours from the last administered dose (5 half-lives). Highly effective contraceptive methods are as follows; intrauterine device, intrauterine hormone-releasing system, bilateral tubal occlusion, vasectomised partner* or sexual abstinence**. Combined or progesterone only hormonal contraception associated with inhibition of ovulation have not been classed as highly effective contraception because it is unknown whether Kineret may interact with hormonal contraceptives and reduce their efficacy. Additionally, any pregnancies reported during the trial will be reported by the Investigator to Manchester CTU as detailed in section 9.6.

^{*} Provided that partner is the sole sexual partner of the WOCBP trial participant and that the vasectomised partner has received medical assessment of the surgical success.

^{**} Refraining from heterosexual intercourse during the entire period of risk associated with the study treatments, which is in line with the preferred and usual lifestyle of the participant. For this trial, the period of risk means from first IMP administration until 30 hours after last IMP administration,

